### 7.2 *Additional Study Evaluation*

Additional assessments that will be reported at each follow-up interval include:

- Type I endoleak, to be assessed by an Independent Core Lab
- Type III endoleak, to be assessed by an Independent Core Lab
- Stent graft migration > 10 mm (compared to 1-month baseline), to be assessed by an Independent Core Lab
- AAA enlargement > 5 mm (compared to 1-month baseline)
- Loss of patency
- Stent fracture, to be assessed by an Independent Core Lab
- AAA rupture
- Conversion to open repair

- Secondary interventions
- AAA-related mortality
- Adverse events, including:
  - Serious adverse events
  - Major adverse events
  - Procedure-related adverse events
  - Device-related adverse events
  - All adverse events, regardless of seriousness or cause

All deaths that occur in the study will be adjudicated by the CEC. AAA related death is any death determined by the CEC to occur as a result of the initial procedure (first 30 days), AAA rupture, conversion to open surgical repair, or any AAA related secondary intervention.

---

## 8.0 DATA ANALYSIS

### 8.1 *Analysis Population*

Primary analyses will be performed on a modified intent-to-treat basis. The modified intent-to-treat group includes all subjects in which the delivery system was inserted into an access vessel. All subjects who achieve technical success and remain free of all other elements of the composite effectiveness endpoint at 12 months will be considered treatment successes. All subjects who fail based on any element of the composite effectiveness endpoint, and all subjects who deemed treatment successes will be included in the denominator. Only subjects with readable imaging during each respective follow-up interval will be included in the denominator for relevant effectiveness endpoints. Subjects not counted as failures, but with incomplete data to assess all the composite elements will be treated as missing data points.

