**Sites are also required to adhere to the reviewing IRB/EC requirements for reporting of SAE's.**

### ***6.13 Major Adverse Events (MAE)***

The following specific events will be considered major adverse events (MAE) for the purpose of evaluating the primary (30 day) and secondary (1 year) safety endpoints:

Major adverse events (MAE) are defined as any one of the following events:

- Death
- Myocardial Infarction
- Stroke (excludes TIA)
- Renal Failure (excludes renal insufficiency)
- Respiratory Failure (excludes COPD or pulmonary complications)
- Paralysis (excludes paraparesis)
- Bowel Ischemia
- Procedural Blood Loss ( $\geq 1,000$  cc)

A major adverse event (MAE) may or may not be considered related to the device. Mortality will be reported as “all cause” and “AAA related.” All deaths occurring in the first 30 days post-index procedure are considered “AAA related.”

The Clinical Events Committee (CEC) shall determine which adverse events are considered Major Adverse Events (MAE) for evaluation of the primary (30 days) and secondary (1 year) safety endpoints.

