### 8.3 *Analysis Methods*

Baseline patient characteristics will be summarized with standard descriptive statistics. Categorical variables will be described with percentages and counts. Continuous variables will be described with means, standard deviations, medians, and ranges.

For evaluation of treatment success at 12 months, all subjects with technical success and freedom from all other elements of the composite endpoint will be considered treatment successes. Subjects who fail based on any element of the composite endpoint, and all subjects deemed treatment successes will be included in the denominator. Subjects not counted as failures due to meeting any element of the composite, but who have incomplete data to assess all the composite elements will be treated as missing data points. Only subjects with readable imaging during each respective follow-up interval will be included in the denominator for relevant effectiveness endpoints. Sensitivity analyses will be performed to assess the impact of missing data on the primary endpoint.

Complete data analysis methods will be prospectively defined in a Statistical Analysis Plan.

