### 8.4 *Study Hypotheses*

Treatment success at 12 months in subjects treated with the Ovation Alto will be compared to a performance goal of 80%.

The primary effectiveness hypotheses are defined as:

- $H_0: \pi \leq 80\%$
- $H_1: \pi > 80\%$ , where

$\pi$  is the expected treatment success rate at 12 months in subjects treated with the Ovation Alto. The primary effectiveness endpoint will be met if the lower limit of the one-sided 95% confidence interval for  $\pi$  is greater than 80%.

Additional outcomes in this study will be reported descriptively, with no hypothesis testing.

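### Does counting every failure but setting aside incomplete non-failures, with the sensitivity analysis left unnamed, undermine the primary result?

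*Combined protocol and SAP*

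**What the plan says.** Section 8.4 defines the tested parameter: pi "is the expected treatment success rate at 12 months in subjects treated with the Ovation Alto". Section 8.1 calls the primary analysis modified intent-to-treat, covering everyone in whom the delivery system entered an access vessel. It then fixes the denominator: "All subjects who fail based on any element of the composite effectiveness endpoint, and all subjects who deemed treatment successes will be included", and "Subjects not counted as failures, but with incomplete data to assess all the composite elements will be treated as missing data points". A further sentence reads "Only subjects with readable imaging during each respective follow-up interval will be included in the denominator for relevant effectiveness endpoints". Section 8.3 repeats these rules and adds "Sensitivity analyses will be performed to assess the impact of missing data on the primary endpoint" and "Complete data analysis methods will be prospectively defined in a Statistical Analysis Plan". The supplied document contains no separate SAP text.

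The composite in section 7.1 has nine elements. Three (type I or III endoleak, migration, enlargement) are read from imaging. The other six (technical success, rupture, conversion, and reintervention for stenosis, occlusion or kink, for thromboembolism, or for fracture) can be failed without a 12-month scan. Death is not on the list, although section 6.13 says "All deaths occurring in the first 30 days post-index procedure are considered" AAA related.

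Section 8.5 gives 92.8% expected success, a goal of 80%, a one-sided exact 95% limit, 86.1% power, 60 evaluable patients and up to 75 enrolled.

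**The concern.** Inclusion depends on outcome. A subject can be a counted failure without the 12-month scan but cannot be a counted success without it, so the observed proportion need not estimate pi. Deaths sharpen the worry: a subject who dies in the first month with no failing element would seem to leave the denominator, and the text does not say whether that is meant. The imaging sentence, if applied to the composite, could also be read as removing a technical failure who never had a scan.

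The decision is a single pass or fail against 80%, and the sample size allows for 15 of 75 subjects being non-evaluable. A pass at 54/60 would be reversed by one extra counted failure. With no method named for the promised sensitivity analysis, a reader of the protocol alone cannot tell how such a result would be tested.

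**Working it through.** **1. The plan's own figure.** Inputs from section 8.5: n = 60, goal 0.80, true rate 0.928, one-sided exact 95% limit. The lower limit is 79.2% at 53/60 and 81.2% at 54/60, so 54 successes are needed. P(X ≥ 54 | 60, 0.928) = 0.8611, which matches the stated 86.1%. P(X ≥ 54 | 60, 0.80) = 0.0308. The sample size is not in error.

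**2. Loss unrelated to outcome.** Let p be the true rate, m the share lost, and f the share of failures established without the 12-month scan. The documents do not give f, so 0, 0.5 and 1 are shown. They do not state m either; 20% is implied by (75 − 60)/75.

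- P(counted success) = (1 − m)p
- P(counted failure) = (1 − p)[f + (1 − m)(1 − f)]

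At p = 0.928, m = 0.2, f = 1, the expected rate is 0.7424/(0.7424 + 0.072) = 91.2%. At p = 0.80 it is 0.64/(0.64 + 0.20) = 76.2%. The bias is downward. To get the chance of passing, sum over n ~ Binomial(75, P(counted)), using the exact threshold at each n:

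| Lost | f | Expected rate at p = 92.8% | Pass chance at 92.8% | False pass at 80% |
|---|---|---|---|---|
| 20% | 0 | 92.8% | 86.5% | 3.4% |
| 20% | 0.5 | 92.0% | 80.6% | 1.5% |
| 20% | 1 | 91.2% | 74.0% | 0.6% |
| 10% | 0 | 92.8% | 91.0% | 3.6% |
| 10% | 0.5 | 92.4% | 88.9% | 2.5% |
| 10% | 1 | 92.1% | 86.7% | 1.7% |

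No false-pass chance reaches 5%. Power falls below 86.1% only at 20% loss with f above zero, and only if 92.8% is a full-cohort rate. Section 8.5 says it came from applying this study's success definitions to the earlier device study. If that included the same denominator rule with similar attrition, there is no shortfall.

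**3. Loss related to risk.** Suppose the true rate is 80% and lost subjects fail at twice the rate of retained ones (assumed). Retained risk is r = 0.20/[(1 − m) + 2m]: 16.7% at m = 0.2 and 18.2% at m = 0.1. Let s be the share of lost subjects' failures that are seen.

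| Lost | s = 0 | s = 0.5 | False pass reaches 5% at |
|---|---|---|---|
| 20% | 11.5% | 3.5% | s = 0.355 |
| 10% | 7.5% | 4.0% | s = 0.333 |

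If none are seen, a smaller contrast is enough. With exactly 60 counted and 15 missing, success of 75% in the missing and 81.25% in the rest (0.2 × 75% + 0.8 × 81.25% = 80%) gives 5.1%.

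**4. How fragile a pass is.** With all 75 classified, 67 successes are needed: the lower limit is 81.6% at 67/75 and 79.99% at 66/75. With 15 missing, x/60 survives k failures among them if x + 15 − k ≥ 67. So 54/60 survives at most 2, 55/60 at most 3, and 56/60 (close to the expected 0.928 × 60 = 55.7) at most 4. If deaths alone are added as failures, 54/60 is reversed by 1 (54/61, limit 79.5%), 55/60 by 2 (55/62, 79.8%) and 56/60 by 4 (56/64, 78.6%; 56/63 still passes at 80.1%).

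**5. The alternative denominator.** Under section 6.8 a subject converted to open repair stays in the study only until 30 days after conversion or discharge, whichever is later. An early conversion would then have no 12-month scan. Requiring a scan of everyone would delete such known failures, which helps the device. Counting them is the more cautious choice.

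**The case for a change.** The strongest case for acting is that the protocol plans for 15 non-evaluable subjects, that one to four reclassified subjects can reverse a pass near the threshold, and that the method, its assumptions and the classification of deaths should be fixed before results are known. The conservative reading depends on loss being unrelated to risk, which is doubtful if deaths are among those set aside.

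Part of this stands. The protocol text does not say how a death without a failing element is classified, and it names no sensitivity method. Step 3 shows that informative loss can favour the device. The calculation also considers only the 12-month scan, whereas migration and enlargement need the 1-month baseline too.

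The rest is weaker. Section 8.3 commits to sensitivity analyses for exactly this purpose and to methods set prospectively in a Statistical Analysis Plan; the absence of that text here does not show that it lacks the detail. The gap on deaths is narrower than it looks. Rupture, conversion and several reinterventions are already failures, so deaths that follow them stay counted, and section 7.2 reports AAA-related mortality separately after committee adjudication. Leaving death out of a device-effectiveness composite is a design choice. As for imaging, sections 8.1 and 8.3 expressly count every failure, and the imaging sentence refers to each follow-up interval and its relevant endpoints, most naturally the interval summaries in section 7.2. Several provisions also limit missing data: the 305–547 day window (8.2), substitute imaging (5.5.1.5), repeated contact attempts (5.3) and the exit assessment (5.5.1.7).

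**Conclusion.** The denominator does depend on outcome, and the rate can differ from pi in either direction, but nothing stated in the plan is wrong. The 86.1% reproduces. Under loss unrelated to outcome, the false-pass chance is 0.6% to 3.6% for 10% or 20% loss. It passes 5% only if lost subjects carry higher risk and most of their failures are unseen: at doubled risk, fewer than about 36% seen (20% lost) or 33% seen (10% lost). The twofold risk, the share seen, f and the loss rates are all assumptions.

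Informative dropout of that kind would remain under any primary denominator, and the obvious alternative of requiring complete imaging would discard known failures. The present rule is a fair trade-off. The unnamed sensitivity method and the classification of deaths are gaps that an analyst would ordinarily fill in the SAP that section 8.3 calls for, for example with a tipping-point count like step 4. Filling them alters neither the primary test nor its decision rule, so no change to the plan follows.

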### 8.2 *Analysis Windows*

Safety and effectiveness data will be categorized into discrete, contiguous analysis windows to ensure that all available data are included in analyses. The analysis windows around each follow-up visit are: 1 month (0-90 days), 6 months (91-304 days), and 12 months (305-547 days).

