The Investigator and/or IRB/EC may require that these events are reported as adverse events. In this case, the Investigator should report these observations based on their medical judgment and requirements of the IRB/EC.

**Device-related adverse events should be reported to the study Sponsor as soon as possible (24 hours recommended), but no more than 10 working days after the date the site becomes aware of the event.**

Device-Related: Event is caused or contributed by any component of the device during delivery, deployment or while the device is in situ post-operatively

- “Caused or Contributed” means that an injury was or may have been attributed to the study device, or that the study device was or may have been a factor in an injury, including events occurring as a result of:
  - Any event resulting from intervention on the AAA or device
  - Any device failure, malfunction, inadequacy, including operator error

Procedure-Related: Event is caused or contributed by the initial study device implantation (index) procedure, up to 30 days, unless a different etiology can be identified

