## 7.0 ENDPOINTS

### 7.1 *Primary Endpoint*

The primary objective of this study is to evaluate treatment success at 12 months with the Ovation Alto Abdominal Stent Graft System in subjects with AAA.

Treatment success will be a composite endpoint comprised of all of the following:

- Technical success\*;
- Freedom from type I & III endoleak at 12 months, to be assessed by an Independent Core Lab;
- Freedom from stent graft migration > 10 mm at 12 months (compared to 1-month baseline) , to be assessed by an Independent Core Lab;
- Freedom from AAA enlargement > 5mm at 12 months (compared to 1-month baseline);
- Freedom from AAA rupture through 12 months;
- Freedom from conversion to open repair through 12 months;
- Freedom from stent graft stenosis, occlusion, or kink requiring secondary intervention through 12 months;
- Freedom from thromboembolic event attributable to stent graft requiring secondary intervention through 12 months, and:
- Freedom from stent fracture requiring secondary intervention through 12 months

\*Technical Success will be a composite endpoint comprised of all of the following:

- Successful delivery, defined as ability to deliver the implant to the intended location without the need for unanticipated corrective intervention related to delivery, using an adjunctive device outside of the Ovation Alto Abdominal Stent Graft System;
- Successful and accurate deployment, defined as:
  - deployment of the endovascular stent graft in the planned location
  - patency of the endovascular stent graft, absence of device deformations (e.g. kinks, stent eversion, mal-deployment, misaligned deployment) requiring unplanned placement of an additional device within the endovascular stent graft, and;
  - successful withdrawal of the delivery system without the need for unanticipated corrective intervention related to withdrawal

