### ***11.2 Clinical Events Committee***

The Clinical Events Committee (CEC) shall be used to review and adjudicate all device related adverse events (AE) and all serious adverse events (SAE) regardless of the relatedness to the device. The CEC shall also determine which adverse events are considered Major Adverse Events (MAE) for evaluation of the primary (30 days) and secondary (1 year) safety endpoints. The committee shall consist of at least three (3) physicians representing multiple specialties familiar with abdominal aortic aneurysm repair. The CEC will provide their review to the DSMB and shall meet annually, at a minimum.

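### Section 8.2 makes the 1-month MAE rate a 90-day rate, while sections 6.13 and 11.2 evaluate MAE at 30 days

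*Combined protocol and SAP*

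**What the plan says.** Section 8.2 states that "Safety and effectiveness data will be categorized into discrete, contiguous analysis windows", and then gives the limits: "The analysis windows around each follow-up visit are: 1 month (0-90 days), 6 months (91-304 days), and 12 months (305-547 days"). It does not separate visit-based measurements from events that have their own date. The stated purpose is that no available data are left out.

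MAE are among the outcomes that section 7.2 reports by interval: "Additional assessments that will be reported at each follow-up interval include". The Protocol Summary does the same and adds that the Clinical Events Committee adjudicates MAE at 1, 6 and 12 months.

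Two other sections use different time points. Section 6.13 defines MAE "for the purpose of evaluating the primary (30 day) and secondary (1 year) safety endpoints". Section 11.2 has the committee decide which events are MAE "for evaluation of the primary (30 days) and secondary (1 year) safety endpoints".

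Five elements of the primary composite in section 7.1 are cumulative, for example "Freedom from AAA rupture through 12 months". The others are conversion, stenosis/occlusion/kink, thromboembolic event and stent fracture, the last three only if they need a secondary intervention. No day is attached to any of them. Section 5.5.1.5 places the 12-month visit at day 365 with an allowance of 60 days either way. Section 8.4 reports all outcomes other than the primary one descriptively. Section 8.3 defers complete methods to a Statistical Analysis Plan, and the combined document contains no separate plan that settles these points.

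**The concern.** Contiguous windows are a sensible way to decide which visit or scan represents a time point. They fit poorly with events that have a known date and are meant to be counted over a fixed period. Under section 8.2 an MAE on day 75 belongs to the 1-month interval, whereas under sections 6.13 and 11.2 it lies outside the 30-day period. These are two stated rules that give different counts for the same subject.

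At stake is the meaning of the safety table. A reader who sees a 1-month MAE rate will take it for the usual 30-day figure and may set it beside 30-day figures from elsewhere, when it could be a 90-day rate. The 1-year figure has the same problem, because the last window closes well after day 365.

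The missing day limit on the cumulative primary elements is a smaller matter. It leaves open how long a subject is watched for failure, and this should not be settled after the data are seen.

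**Working it through.** **1. Inputs.** Windows: days 0-90, 91-304 and 305-547 (section 8.2). MAE time points: 30 days and 1 year (sections 6.13, 11.2). Visits: 30 ± 14 = days 16-44 and 365 ± 60 = days 305-425 (section 5.5.1.5). Enrollment: up to 75, with 60 evaluable required (section 8.5).

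**2. The plan's own figure.** Section 8.5 states 86.1% power for a true rate of 92.8% against 80% with 60 evaluable subjects and a one-sided exact 95% limit. The exact lower limit is 81.2% for 54/60 and 79.2% for 53/60, so 54 successes are needed. P(X ≥ 54 | n = 60, p = 0.928) = 0.8611, which agrees. The MAE point does not touch this calculation.

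**3. Length of the windows.** 1 month: 90/30 = 3.0 times the 30-day period, or 90 − 30 = 60 extra days. 12 months: 547 − 365 = 182 days past day 365. With on-schedule visits the excess is at most 425 − 365 = 60 days. The remaining 547 − 425 = 122 days come into play only if a visit falls outside its allowance.

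**4. Size of the MAE effect.** Let b be the share of subjects with an MAE by day 30 and h the monthly rate of first MAE afterwards. The documents give neither, so both are assumptions: b = 2-8%, h = 0.25-1%. A month is 30.4375 days. The addition from days 31-90 is

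(1 − b) × [1 − (1 − h)^(60/30.4375)].

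- Low end, b = 0.08, h = 0.0025: 0.92 × 0.00492 = 0.0045. Times 75 subjects: 0.34.
- High end, b = 0.02, h = 0.01: 0.98 × 0.01962 = 0.0192. Times 75 subjects: 1.44.

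The addition is therefore about 0.5-1.9 percentage points, or 0.3-1.4 subjects.

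**5. Is there an endpoint behind the 30-day wording?** Sections 6.13 and 11.2 speak of a primary 30-day and a secondary 1-year safety endpoint. Section 7.1 has one primary endpoint, the 12-month effectiveness composite, and section 7.2 lists MAE without a day. The 30-day and 1-year references therefore point to endpoints that section 7 does not define.

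**6. A strict day-365 limit for the primary composite.** Suppose 12-month visits are spread evenly over days 305-425. Mean observation to the visit is day 365. Truncating at day 365 leaves the early half at a mean of day 335 and puts the late half at day 365, so the mean becomes (335 + 365)/2 = day 350. In addition, a subject who ruptures or converts on day 400 before a 12-month CT would be event-free at day 365 with no 12-month image. Sections 8.1 and 8.3 treat such a subject as missing, so a known failure would leave the denominator.

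**The case against.** Section 8.2 describes its windows as lying around visits and gives a purpose for them, so it is a prespecified convention and not an oversight. The 30-day text refers to endpoints that section 7 does not contain, the outcomes are descriptive, and a Statistical Analysis Plan is promised. Much of this stands: it limits the point to descriptive reporting, and if that plan counts events by date, section 8.2 only needs aligning with it. It does not remove the conflict, because section 8.2 names safety data expressly and no section exempts dated events.

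The day-30 rules for attribution are not further evidence of conflict. Section 6.11 defines a procedure-related event as "Event is caused or contributed by the initial study device implantation (index) procedure, up to 30 days", and section 6.13 says "All deaths occurring in the first 30 days post-index procedure are considered" AAA-related. Both classify by event date, whatever window the event falls in.

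A reader might infer three stronger things that the documents do not support.

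- *The primary test is compromised or its power reduced.* Counting failures after day 365 can only lower the success rate, so it works against meeting the goal and does not inflate type I error. A power loss cannot be put in figures: section 8.5 derives 92.8% from the earlier device study without giving a day limit, and no late failure rate is stated.
- *Section 5.0 supplies a competing limit for the primary composite.* Its mention of 12-month follow-up describes the secondary objectives.
- *A baseline CT as late as day 90 would be accepted for migration and enlargement.* Sections 6.2 and 6.7 tie the CTs to scheduled visits, and the 1-month visit is days 16-44. The inference holds only if the follow-up interval in sections 8.1 and 8.3 means the section 8.2 window, which they do not say.

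**Conclusion.** The conflict over MAE is real and should be corrected. As written, section 8.2 gives a 1-month MAE rate over 90 days, while sections 6.13 and 11.2 call for 30 days. The threefold difference in period follows directly from the stated limits. The addition of about 0.5-1.9 percentage points rests on assumed rates and is only a guide to scale. The consequence is a mislabelled descriptive safety rate, with no effect on the hypothesis test, the sample size or the stated power. The undefined safety endpoints in 6.13 and 11.2 are part of the same inconsistency.

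The lack of a day limit on the five cumulative primary elements is a minor gap whose effect is conservative. It calls for a definition fixed in advance. It does not justify a strict day-365 limit for the primary analysis, which could turn a known failure into a missing value.

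**What to change.** - In section 8.2, state that the windows assign visits and images to time points and do not apply to dated events.
- Report MAE and deaths by actual event date, to day 30 and to day 365, with the at-risk denominator stated for each. The denominator rule should cover subjects who exit before the cut-off, including those whose permitted 12-month visit falls on days 305-364 and those who leave after conversion under section 6.8.
- Reconcile sections 6.13 and 11.2 with section 7: either list the 30-day and 1-year MAE rates there as descriptive outcomes or remove the references to safety endpoints.
- For the five cumulative elements in section 7.1, state one limit before the data are seen. It should be such that a known rupture, conversion or qualifying secondary intervention up to the subject's 12-month assessment stays a failure in the denominator. Report the count to day 365 as a sensitivity analysis.

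The cost is a change of wording and a small amount of extra analysis. Section 10.10 already requires dated visit notes and diagnostic reports and adverse event source records, so no new data collection should be needed. The sample size, the significance level and the 80% decision rule stay as they are.
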